## **23 AGENT ADMINISTRATION**

### **23.1 Sulindac**

Study agent (sulindac tablets, 150 mg active) will be self-administered according to investigators' instructions, including taking the tablets with a meal and not within one hour of reclining or sleeping. The usual adult dose is 150 or 200 mg bid taken with meals, and the maximum daily dose is 400 mg. Toxicities associated with sulindac are those consistent with other NSAIDs. The most common side effects are gastrointestinal and include, but are not limited to, abdominal pain, cramping, nausea, gastritis, and even serious gastrointestinal bleeding and liver toxicity.

## **24 TOXICITY MONITORING AND RESPONSE PLAN**

Note: Risk for toxicity with sulindac increases with longer use ( $\geq 6$  months) and higher doses. Dose reductions of 50% to 150 mg qd will be allowed, and 2 drug holidays totaling no more than 4 weeks will be permitted. Participants will be advised not to use over-the-counter NSAIDs without first consulting study staff.

- a. Participants will receive a study log on which to record time of sulindac doses. Participants will be instructed to use the study log daily to record concomitant medication use and adverse events. Participants will be instructed to return the log at their 3 month visits for adverse event review and concomitant medication review by nurse coordinator.

- b. During the initial 6 weeks of heaviest in-home blood pressure monitoring, site study personnel will place telephone calls every two weeks ( $\pm 3$  days) to document these data reducing to monthly after the first 6 weeks on agent.
- c. Participants will be educated to contact us at any time during the study to report any adverse event that fails to resolve in 3 days or results in a visit to the doctor or hospital.
- d. Participants with two or more BP readings above 140/90 will be seen by the research nurse and evaluated for antihypertensive therapy.
- e. Participants who develop grade 2 hypertension as determined by CTCAE version 4.0 will be monitored more closely and offered dietary and/pharmacologic intervention. Participants who develop grade 3 or higher hypertension will be removed from study, and treated as medically indicated to control their blood pressure.
- f. Participants experiencing a  $\geq$  Grade 2 toxicity (NCI, CTCAE version 4), regarded as possible, probable or definitely related to study agent during the study agent administration period will suspend the study agent(s) for a maximum of 2 consecutive days per event.
- g. With any NSAID trial, GI upset requiring dose reductions or the temporary need to take an NSAID may arise. Dose reductions of 50% to 150 mg qd will be allowed until symptoms resolve or indefinitely, and 2 drug holidays totaling no more than 4 weeks will be permitted during the study period.
- h. If the event remains unresolved at lower dosing, the participant will discontinue study agent and end of treatment procedures will be performed.
- i. If the event resolves, the participant will resume the original study schedule.
- j. Study agent will be discontinued if the same event which caused suspension of the study agent occurs more than twice during the study.
- k. Participants that miss  $>28$  days of study agent during the study agent administration period, regardless of cause, will discontinue study agent and proceed with end of treatment procedures.
- l. Participants experiencing a  $\geq$  grade 2 toxicity possibly, probably, or definitely related to study agent will reduce dose by 50% if symptoms resolve within 7 days. If the symptoms recur on lower dose, the subject will be withdrawn from study and proceed with end of treatment procedures.
- m. Only one dose modification will occur in this study.

For the observational group, there is no toxicity or risk associated with this study. Thus participants will not be followed past conclusion of the study. No toxicity data will be collected and no adverse events are to be expected.

## 25 END OF TREATMENT PROCEDURES

- a. Vital signs (Blood pressure, pulse);
- b. Hematology (CBC/differential and platelet count);
- c. Chemistry panel (to include Urea Nitrogen, Creatinine, ALT, AST)
- d. Urinalysis
- e. Review concomitant medications;
- f. Review adverse events [apply only to AI Sulindac arm];
- g. Return unused tablets/empty sulindac bottle [apply only to AI Sulindac arm];

End of Treatment procedures will be performed within 28 days of the study agent(s) administration period. For participants who are withdrawn from the study during off study agent(s) period, end of treatment procedures will be performed within 7 days of the date of withdrawal.

[figure not shown]
Following discontinuation of study agent participants experiencing adverse events will be contacted weekly by telephone or clinic visit until resolution or stabilization of condition. Abnormal laboratory values will be followed every 14 days until resolution or one month post last dose of study agent(s) whichever occurs first.

## 26 DRUG FORMULATION AND PROCUREMENT

### 26.1 Sulindac

#### 26.1.1 Physical and Chemical Characteristics

Sulindac is a non-steroid, anti-inflammatory indene derivative designated chemically as (Z)-5-fluoro-2-methyl-1-[[p-(methylsulfinyl)phenyl] methylene]-1H-indene-3-acetic acid. It is not a salicylate, pyrazolone or propionic acid derivative (Figure 4). It has a molecular weight of 356.42 and is a yellow crystalline compound which is a weak organic acid practically insoluble in water below pH 4.5 but very soluble as the sodium salt or in buffers of pH 6 or higher. Sulindac is available in 150 mg and 200 mg tablets for oral administration.

#### 26.1.2 Inactive ingredients

Cellulose, magnesium stearate, starch.

#### **26.1.3 Availability**

Sulindac is readily and commercially available in 150 mg and 200 mg tablets for oral administration. Generic sulindac will be obtained from the Arizona Cancer Center UMC North Outpatient Pharmacy and Stony Brook Hospital Investigational Pharmacy from the pharmaceutical supplier of their choice. Study agent will be stored in the Arizona Cancer Center UMC North Outpatient Pharmacy and Stony Brook Hospital Investigational Pharmacy.

#### **26.1.4 Agent Distribution**

Sulindac distributions to the study coordinator for study participants will follow receipt of a prescription signed by a study physician.

#### **26.1.5 Agent Accountability**

Arizona Cancer Center UMC North Outpatient Pharmacy and Stony Brook Hospital Investigational Pharmacy must maintain a careful record of the inventory and disposition of all agents received using the NCI Drug Accountability Record Form (DARF) or similar record. Duties include maintaining adequate records of receipt, dispensing and final disposition of study agent(s). This responsibility has been delegated to [name], Pharm. D., and designated UACC and SBCC pharmacy staff. Include on receipt record from whom and to whom study drug was shipped, date, quantity and batch or lot number. The study coordinator will maintain source document, and note quantity and date study agent are dispensed to and returned by each participant.

#### **26.1.6 Packaging and Labels**

Sulindac will be purchased in bulk as 150 mg tablets and packaged into individual bottles containing 180 tablets each or as requested by the study nurse. Bottles will be labeled with participant name and address, study and drug identifying information, dosing instructions, pharmacy information along with pharmacist identifier, a contact phone number, and the participant number will be added to the label prior to distribution to the participant.

#### **26.1.7 Storage**

Study medication will be stored at room temperature (59° to 86° F), protected from environmental extremes and in a locked cabinet or room prior to being issued to participants. Participants will be instructed to store the study agent under similar conditions and out of reach of minor children.

### **27 STATISTICAL CONSIDERATIONS**

#### **27.1 Observation Group**

We will enroll 75 women with the expectation that 60 will complete the entire observation period of 12 months with all MRI measures for the purposes of providing a comparison (non-placebo) for our open-

label, single arm study of sulindac in breast cancer patients receiving aromatase inhibitors in the adjuvant setting for the prevention of breast cancer recurrence. The observational arm will control for the unknown effects of AI as well as time on BD as measured by fat/water and diffusion-weighted magnetic resonance imaging (MRI), patient reported outcomes, effects of sulindac on AI adherence and provide additional information on use of NSAIDs in patients on AIs generally. This request is being made as a consequence of having to redesign our trial from randomized to non-randomized, open label when the study section recommended, and NCI accepted, a cut to the 5th year of funding. This significantly impacted the available funds to cover costs of acquiring the placebo and required a reduction in sample size to complete accrual to the study. The slope between 0 and 12 months that includes measures at 0, 6 and 12 months will be estimated using linear regression analysis (to allow for the possibility of slight variability in the timing of the measurements).

Statistical analysis for the imaging primary endpoints will initially estimate the slope between 0 and 3 months (no study drug) and the slope across 3, 9 and 15 months (sulindac treatment) separately for each woman. The slope between 0 and 3 months is the difference between the two measurements (divided by the time interval), while the slope while on sulindac will be estimated using linear regression analysis (to allow for the possibility of slight variability in the timing of the measurements). Preliminary analysis will assess whether the pattern of change with sulindac treatment is linear. Mean slopes and 95% confidence intervals will be estimated for the baseline (no study drug) and sulindac treatment periods. Comparisons of the mean slope with and without sulindac will be performed using a paired t test since the imaging endpoints as Fra50 from FWR-MRI (Aim 1 and primary trial endpoint) and ADC from DW-MRI (Aim 2) will be restricted to images from the unaffected, contralateral breast. The BPI-SF measure of past-week worst pain is a discrete, ordinal value. Statistical analysis will proceed using a proportional odds model with a robust variance estimate to account for potential correlation among measures in the same woman. The independent variable will be time; differences in the values observed during the baseline and sulindac treatment periods will be estimated using a linear contrast of the estimated coefficients. Adjustment for the inflated alpha level due to the use of three primary study endpoints (FWR-MRI, DW-MRI, and BPI-SF) will be performed using the Bonferroni correction. The incidence of any  $\geq$  grade 2 hypertensive adverse events will be compared during the baseline and sulindac treatment periods using McNemar's test. Since this is a safety endpoint, no multiple comparisons adjustment of the alpha level will be performed.

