**Figure 1. Study schema and primary measurements to be conducted during the sulindac intervention study.** All participants will have an initial one-month washout period prior to a 3-month observation period during which they will discontinue NSAID use and be monitored for adherence to the trial and undergo baseline MR imaging at two time points. For the intervention period, participants will undergo MR imaging after initiating sulindac at 6 and 12 months. Participants will complete the participant reported outcome (PRO) questionnaires, return drug logs, undergo standard laboratory testing, and receive additional study drug at these visits. Blood and urine as well as clinical measures of blood pressure will be obtained at baselines, and at 3-, 6-, 9- and 12-month on sulindac to bank for analysis of metabolite levels and prostanoids. In those who consent, breast biopsies will be obtained at baseline 2 and after 6-month on sulindac for exploratory analyses of proliferation, apoptotic, cellular and whole genome expression changes in response to agent.

month observation no NSAID period, will be used to identify participant likely not to adhere to the study

regimen and to determine the extent of variability in BD over time. **The study schema for the sulindac intervention is shown in Figure 1.**

#### 4.2 Objective 2

In addition to the intervention arm, a total target population of 75 breast cancer patients, matched on characteristics to the sulindac intervention study, are being recruited to an observation arm (hereafter referred to as 'observation' group) for the primary purpose of determining change in BD while on AI for 12 months as determined by our novel MRI-based imaging approach to generate a non-radiative, non-contrast of a fat to water map of the breast using FWMRI.

In healthy postmenopausal women, the mean age-related change in BD by mammography at 2-yrs has been reported from randomized trials to be -1.3% ( $\pm 2.9\%$ ). Studies of women on AIs have shown that AI use for 12 months does not *significantly* decrease BD beyond that of the age-related change in the contralateral breast of breast cancer patients when compared to a placebo control (see Table 1).

Table 1. Effect of Aromatase Inhibitors on Breast Density in Randomized Studies

Study	Agent	Mean change in BD	P value	Summary
Vachon et al. 2007 (Vachon et al. 2007)	Letrozole	-2.7%	p=0.96	No statistically significant therapy-by-subgroup interactions (for BMI and age at entry)

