## 7.3 Primary specific aims

- a. Compare change in BD as measured by MRI-acquired fat-to-water ratio (FWR-MRI) in the *contralateral, unaffected breast pre- and post-sulindac* (primary trial endpoint).

Hypothesis: Women treated with AI + sulindac 150 mg bid will show a greater decrease in BD over 12 months when compared to their baseline change measurement.

- b. Compare pain scores using the Brief Pain Inventory-Short form (BPI-SF) *pre and post sulindac*.

Hypothesis: Women treated with AI + sulindac 150 mg bid will experience reduced pain scores over 12 months when compared to their baseline change measurement.

- c. Compare mean arterial blood pressure within individuals.

Hypothesis: Administration of 150 mg bid sulindac for 12 months to women on AIs will not lead to a clinically significant (Grade 2 or higher) increase in blood pressure when compared to their baseline change measurement.

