## 15 PARTICIPANT ELIGIBILITY

### 15.1 Eligibility criteria:

- a. Postmenopausal women with of first incidence of early stage (stages 0 – III) hormone receptor positive breast cancer stabilized on aromatase inhibitor (AI) therapy for at least 3 months
- b. Patients must have started on AI at least three months before consenting with plans to continue on AI therapy for a minimum of 16 months (12 months for AI only arm) or until the end of the study intervention.
- c. Patients must have an unaffected, non-irradiated contralateral breast with a baseline BD score of  $\geq 25\%$  as measured by standard digital mammography (BIRADS score  $\geq 2$  or scattered fibroglandular densities at least heterogenous or greater) performed within 12 months of consent to the study
- d. A willingness to follow the study protocol, as indicated by provision of informed consent to participate
- e. A willingness to avoid taking NSAIDs outside of the trial (rare NSAID use for musculoskeletal symptoms accepted, and/or daily use of aspirin < 81 mg is allowed for the duration of the study) [apply only to AI Sulindac arm]

- f. Normal renal function as determined by a serum creatinine  $\leq$  upper limit of normal (ULN= 1.5mg/dl) or a creatinine clearance above 60 ml/min [apply only to AI Sulindac arm]
- g. No known contraindication to NSAID use [apply only to AI Sulindac arm]
- h. Normotensive or controlled blood pressure (< 140/90) on no more than two anti-hypertensive medications [apply only to AI Sulindac arm]

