## **15.2 Exclusionary criteria:**

- a. Current or anticipated need for daily aspirin or NSAID. Daily use of no more than 81 mg of aspirin for cardiovascular protection is permitted.
- b. Known intolerance to NSAIDs [applies only to AI + Sulindac arm]
- c. Age  $\geq$  75 years
- d. History of cardiovascular disease including prior myocardial infarction, angina, stroke, or transient ischemic attack (TIA) [applies only to AI + Sulindac arm]
- e. Diabetes requiring drug therapy [applies only to AI + Sulindac arm]
- f. Current smoker [applies only to AI + Sulindac arm]
- g. Current uncontrolled hypertension [applies only to AI + Sulindac arm]
- h. Blood pressure > 140/90 at baseline by home monitoring [applies only to AI + Sulindac arm]
- i. History of GI bleeding in the past 5 years. [applies only to AI + Sulindac arm]
- j. Patients with active GI symptoms including burning pain in the middle of the stomach between meals or at night, stomach bloating, heartburn, nausea or vomiting despite PPI therapy. [applies only to AI + Sulindac arm]
- k. History of a bleeding diathesis or current anticoagulant therapy [applies only to AI + Sulindac arm]
- l. History of claustrophobia
- m. Have electrically, magnetically, or mechanically activated implants including cardiac pacemaker, cochlear implants, magnetic surgical clips or prostheses.
- n. Current use of any corticosteroids or immune suppressive therapies [applies only to AI + Sulindac arm]

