All screening and pre-washout evaluations will be completed within 21 days of initiating the study Week 1 Day 1 of the study schedule. As the target population will be postmenopausal, no serum pregnancy test will be performed.

The following events will occur at screening/baseline visits for participants in the sulindac treated group.

- a. Medical history including demographics (race, ethnicity, age, and etc.);
- b. Review medication use within the past 30 days;
- c. Review concomitant medication and supplement use;
- d. Vital signs (Blood pressure, pulse);
- e. Height and weight;
- f. Hematology (CBC/differential and platelet count);
- g. Chemistry panel (to include Urea Nitrogen, Creatinine, ALT, AST)
- h. Urinalysis
- i. Fecal occult blood test
- j. Participants will undergo a 30 day NSAID washout period.
- k. Participant may be reevaluated for study participation after the washout period.
- l. Screening/baseline lab work will be collected after the washout period.
- m. FWR-MRI and DW-MRI of contralateral, unaffected breast, quality of life questionnaire (FACT-G) and pain measurements using BPI-SF and WOMAC instruments. Participant will be given a

validated, semiautomatic electronic home blood pressure monitoring device to measure their blood pressure in each morning and evening for 3 days every 2 weeks for the first 6 weeks right after the washout period.

The following events will occur at screening/baseline visits for participants in the control arm.

- a. Medical history including demographics (race, ethnicity, age, and etc.);
- b. Review medication use within the past 30 days;
- c. Review concomitant medication and supplement use;
- d. Vital signs (blood pressure, pulse);
- e. Height and weight;
- f. Blood and urine samples obtained for research biomarkers.
- g. FWR-MRI and DW-MRI of contralateral, unaffected breast, quality of life questionnaire (FACT-G) and pain measurements using BPI-SF and WOMAC instruments

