## **21 TREATMENT PLAN AND EVENTS**

### **21.1 Sulindac treated group**

Clinic visits will be scheduled at 3-month intervals ( $\pm 28$  days), during which a focused physical exam, FACT-G, pain measurements (BPI-SF and WOMAC), and indicated laboratory tests (CBC, chemistry panel) will be performed. At each visit, unused study agents will be collected, counted, and returned for appropriate disposal.

The following on study events will occur.

- a. Participants will receive and complete study log (calendar)
- b. Participants will be given a validated, semiautomatic electronic home blood pressure monitoring device to measure their blood pressure in each morning and evening for 3 days every 2 weeks for the first 6 weeks on agent and in last 6 weeks of therapy.
- c. Sulindac 150mg b.i.d. will be self-administered, by mouth, daily for a total of 12 months
- d. A chemistry panel (to include Urea Nitrogen, Creatinine, ALT, and AST) and hematology (CBC/differential and platelet count) will be performed at the post-washout, post-observation, 6 months and 12 months on sulindac visits.
- e. Blood for serum sulindac and metabolites levels will be obtained at baseline (both post-washout and post-observation visits) and at months 3, 6, 9 and 12 on sulindac.
- f. Blood pressure will be measured in the clinic at all clinic visits.
- g. Blood pressure will be monitored at home.

- h. The FACT-G, BPI-SF and WOMAC instruments will be administered at 3, 6, 9 and 12 months' clinic visit.
- i. A breast core biopsy at baseline 2 and 6 months on sulindac for planned biomarker studies and storage for future studies.
- j. Non Contrast breast MRI will be obtained at baseline, post observation and months 6 and 12 on sulindac.
- k. Unused tablets and/or empty sulindac will be returned at study visits for pill count.
- l. A urine sample for research biomarker studies will be obtained at baseline (post-washout and post-observation visits) and at 3, 6, 9, and 12 months on sulindac.
- m. A +/- 28 days window will be allowed for specimen collection and all procedures.

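### McNemar's test of grade 2 or higher hypertension sets three to four no-drug months against twelve months on sulindac without exposure adjustment, so it leans towards an apparent increase

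*Protocol*

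**What the plan says.** Aim (c) in protocol 7.3 is a within-woman blood-pressure comparison. Its hypothesis is that 12 months of sulindac "will not lead to a clinically significant (Grade 2 or higher) increase in blood pressure when compared to their baseline change measurement". The test is in 27.1: the incidence of any ≥ "grade 2 hypertensive adverse events will be compared during the baseline and sulindac treatment periods" using McNemar's test, with no multiplicity adjustment. Neither period is given a start, an end or a length for this endpoint. The only baseline length in that section belongs to the MRI analysis, which "for the imaging primary endpoints will initially estimate the slope between 0 and 3 months (no study drug"); those slopes are divided by time. Section 7.2 describes a 1-month washout, then 3 months of observation, then 12 months of sulindac.

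Blood-pressure monitoring is also uneven:
- **Home readings before drug:** one block, "every 2 weeks for the first 6 weeks right after the washout period" (section 20).
- **Home readings on drug:** two blocks, "for the first 6 weeks on agent and in last 6 weeks of therapy" (21.1).
- **Clinic readings:** per the Figure 1 caption, "clinical measures of blood pressure will be obtained at baselines, and at 3-, 6-, 9- and 12-month on sulindac".

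Entry to the sulindac arm requires "Normotensive or controlled blood pressure (< 140/90) on no more than two anti-hypertensive medications" (15.1) and excludes "Blood pressure > 140/90 at baseline by home monitoring" (15.2).

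Section 27.2 powers the test at 77% for 75 women, with 9% positive on sulindac only against 1% at baseline only, one-sided 5%. It does not mention that the periods differ in length. The SAP gives blood pressure secondary emphasis and specifies no hypertension test.

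**The concern.** McNemar's null hypothesis is that the two discordant cells are equal. For an endpoint of the form 'any event in the period', that holds without a drug effect only if both periods offer the same chance of recording an event. Here one period is three to four times as long as the other, so equal cells is the wrong null. A nominally significant result could not be separated from longer follow-up.

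This is the event test for one of the primary aims, and it concerns safety. The observation group cannot serve as a reference, because section 24 says that no toxicity data are collected there.

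**Working it through.** **Inputs from the documents.** n = 75; discordant shares 9% and 1%; one-sided α = 0.05; stated power 77% (27.2). No-drug time is 3 months, or 4 with washout; on-drug time is 12 months (7.2). The SAP moved the primary analysis to 40 completers, so n = 40 is shown too, although no n is stated for hypertension.

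**Method.** Let p10 be the share positive on sulindac only and p01 the share positive at baseline only. The number of discordant women is m ~ Bin(n, p10 + p01). Given m, the number positive on drug only is b ~ Bin(m, p10/(p10 + p01)), and c = m − b. The uncorrected test rejects if (b − c)/√m ≥ 1.645. The exact test rejects if P(Bin(m, ½) ≥ b) ≤ 0.05. Summing over m and b gives the rejection probability.

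**The plan's own figure.** With p10 = 0.09, p01 = 0.01 and n = 75, power is 77.1% uncorrected and 60.3% exact. The stated 77% therefore matches the uncorrected test. As a check, equal cells of 5% each give false rejection of 5.0% uncorrected and 1.9% exact.

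**No drug effect.** The documents give no background rate, so I assume a 3-month incidence of 1%, a constant hazard and independent windows. Then p_on = 1 − (1 − p_base)^ratio, p10 = p_on(1 − p_base) and p01 = p_base(1 − p_on). For 12:3, p_on = 1 − 0.99⁴ = 3.94%, p10 = 0.0394 × 0.99 = 3.90% and p01 = 0.01 × 0.9606 = 0.96%. The 12:4 row keeps the same monthly hazard, so p_base = 1 − 0.99^(4/3) = 1.33%. In the last two rows, the 1% is the incidence found in the baseline monitoring.

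| Opportunity, on drug : baseline | p10 | p01 | Ratio | False rejection, n = 75 (uncorrected / exact) | False rejection, n = 40 |
|---|---|---|---|---|---|
| 12:3 months | 3.90% | 0.96% | 4.1 | 31% / 9% | 14% / 1.4% |
| 12:4 months | 3.89% | 1.28% | 3.0 | 25% / 8% | 13% / 1.2% |
| 2:1 home blocks | 1.97% | 0.98% | 2.0 | 9% / 0.8% | 3% / 0.1% |
| 4:3 clinic visits, screening counted | 1.32% | 0.99% | 1.3 | 3.8% / 0.2% | 1.1% / <0.1% |

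**Sensitivity to the assumed rate.** For 12:3 at n = 75, a 3-month incidence of 0.5% gives 13% / 1%, and 2% gives 51% / 33%. At n = 40 the figures are 4% / 0.1% and 32% / 10%. Allowing risk to vary between women (gamma frailty, variance 2) leaves the expected discordant ratio at 3.2 to 5.0 for the 3- and 4-month baselines.

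The 2:1 row takes the second on-drug home block as the last 6 weeks (21.1). Section 10.6 says the last month, which would make the ratio 10:6 weeks, about 1.7. Those two passages need reconciling.

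**The case against.** **Detection may follow scheduled checks rather than calendar time.** Section 20 lists blood pressure at screening and baseline visits, and 14.2.1 separates enrolment from the two baseline visits. That makes about three clinic checks before drug against four on drug. Section 30.1 has all adverse events recorded and does not restrict this to the on-drug period. This stands: it is why the lower rows of the table matter. A reader might infer that baseline events go unrecorded; the documents do not say so.

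**Blood pressure does not rest on this test alone.** Section 27.4 compares slopes of home arterial pressure on treatment and at baseline, then intercepts if the slopes do not differ, and gives 80% power for a 4 mm Hg rise in mean arterial pressure. A longer window does not inflate that comparison as it inflates an any-event count. This also stands, but the analysis is labelled secondary and does not repair the event test.

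**The size is assumed.** This stands. A reader might take the 10% discordance in 27.2 as the no-effect rate and conclude that about half of such trials would falsely show harm (53% uncorrected at 12:3, n = 75). The plan states 10% for its 9% against 1% alternative, so it does not support that reading. Nor is the 1% in 27.2 a background incidence: it is a baseline-only share.

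**On-drug capture may be dampened.** Dropout, early stopping and treatment of raised pressure all reduce the lean. Planned dropout of up to 20% does not bring 12 months near 3 or 4.

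**Conclusion.** The point holds as a bias in direction whose size is uncertain. Either reading of the baseline is shorter than 12 months, so with no drug effect the expected discordant ratio exceeds 1 whichever is chosen. Inflation of the one-sided error ranges from none (exact test at low incidence, or detection tied to clinic visits) to about 31% at 1% three-month incidence with the uncorrected test and 75 women, and higher if events are commoner. These figures rest on an assumed background rate, constant hazard and independent windows. The entry rules probably add to the lean, but their timing, and how 140/90 maps to grade 2, are not given.

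The consequence is limited. The error over-calls harm, does not touch the breast-density analysis, and is tied to no stopping rule. It takes effect only if the protocol's test is performed; the SAP omits the test without saying that it was dropped. A reader might infer that the 77% power is miscalculated. It is not: it reproduces, but it assumes equal opportunity in the two periods.

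**What to change.** 1. In 27.1, define the baseline window for hypertensive events and state when their recording starts. Replace the raw McNemar comparison with grade 2 or higher hypertensive events (or first events) per person-month in each period. Give the within-woman rate ratio or difference with its 95% CI, as an estimate, keep all 12 on-drug months, and read it alongside the arterial-pressure slopes.
2. State that the baseline blood-pressure entry rules may leave a residual lean towards an increase.
3. In 27.2, say that the 77% assumes the uncorrected test and equal opportunity in both periods, and replace it with the expected precision at the actual n.
4. Reconcile protocol and SAP on whether this comparison is performed.

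An equal-window McNemar test (baseline against the first 3 months on drug) is optional only. If the planned 9% accrues evenly, the comparison is 2.25% against 1%, and power at n = 75 is about 12% uncorrected or 1.4% exact. It also discards months 4 to 12.

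The cost is wording and a little analysis of data already planned, plus an openly wide interval. For example, 75 women give 75 × 12 = 900 and 75 × 3 = 225 person-months. Seven events against one is 7.8 against 4.4 per 1000 person-months, a ratio of 1.75. Exact binomial limits on 7/8, turned into odds and divided by 900/225 = 4, give a 95% CI of 0.22 to 79.
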